8.6.3 SAE reporting

To ensure participant safety, every SAE, regardless of causality, occurring after the participant has provided informed consent and until 30 days after the last study visit must be reported to Novartis safety immediately, without undue delay, but under no circumstances later than within 24 hours of obtaining knowledge of the events (Note: If more stringent, local regulations regarding reporting timelines prevail). Any SAEs experienced after the 30 day period should only be reported to Novartis Safety if the investigator suspects a causal relationship to study treatment, unless otherwise specified in local regulations. Any SAEs reported up to the last study visit will be reported in the eCRF. SAEs beyond that date will only be recorded in the Novartis Safety database. Detailed instructions regarding the submission process and requirements are to be found in the Investigator folder provided to each site.

Information about all SAEs is collected and recorded on the electronic Serious Adverse Event Report Form; all applicable sections of the form must be completed in order to provide a clinically thorough report.

All follow-up information for the SAE including information on complications, progression of the initial SAE and recurrent episodes must be reported as follow-up to the original episode immediately, without undue delay, but under no circumstances later than within 24 hours of the Investigator receiving the follow-up information (Note: If more stringent, local regulations regarding reporting timelines prevail). An SAE occurring at a different time interval or otherwise considered completely unrelated to a previously reported one must be reported separately as a new event.

If the SAE is not previously documented in the Investigator's Brochure or Package Insert (new occurrence) and is thought to be related to the study treatment, a CMO & PS Department associate may urgently require further information from the Investigator for health authority reporting. Novartis may need to issue an Investigator Notification (IN) to inform all Investigators involved in any study with the same study treatment that this SAE has been reported.

Suspected Unexpected Serious Adverse Reactions (SUSARs) will be collected and reported to the competent authorities and relevant ethics committees in accordance with European Union (EU) Clinical Trial Regulation 536/2014 or as per national regulatory requirements in participating countries.

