9.3 Primary endpoint(s)/estimand(s) analysis

9.3.1 Definition of primary endpoint(s)

The primary objective of the study is to assess the long-term safety and tolerability of ligelizumab in participants with food allergy for an additional three year period after a core study.

Primary endpoints are overall incidence and exposure-adjusted occurrence rates of treatmentemergent adverse events (TEAEs) and serious adverse events (TESAEs).

TEAEs are defined as events that either: 1) started after the first dose of study treatment and within 16 weeks after the last study treatment; or 2) began prior to the first dose of study treatment but increased in severity (based on preferred term) within 16 weeks after the last study treatment.

For all safety analyses, the safety sets defined in Section 9.1 will be used. All participants enrolled into the extension study, regardless of which preceding studies they came from, will be included in the safety analysis. All listings and tables will be presented by treatment dose. All data will be included in the analysis, regardless of rescue medication use.

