10.7.5 Evaluation parameters of the OFC

Objective symptoms exhibited by participants should be evaluated through physical examination. Complaints arising from the participant without observable changes will be classified as subjective.

The OFC will be considered **positive** with the occurrence of any dose-limiting symptom(s). Dose-limiting symptoms indicate a true allergic reaction occurring during the administration of a single dose that should preclude the administration of any further doses. Investigators should refer to Table 10-9 (CoFAR grading scale) for the definition of dose-limiting symptoms. Symptoms can be mild, moderate or severe. Mild symptoms are not usually considered dose-limiting, although a combination of mild symptoms during a single dose might lead to the cessation of the OFC at the discretion of the investigator. All moderate and severe symptoms as defined in Table 10-9 are considered dose-limiting.

Symptoms requiring administration of any rescue medication (e.g., SABA, epinephrine or other) are considered dose-limiting. In this case, the challenge has to be stopped, and the challenge is considered positive.

All findings that the investigator classifies as reactions to the OFC should be recorded in source documentation and on a designated eCRF. These events should not be reported on the Adverse Event eCRF unless they constitute an SAE according to the investigator's judgement.

The details and start time of any treatment and/or medication provided to treat OFC-related allergic reactions should be recorded on the respective eCRF. The OFC will be considered **negative** if a participant does not exhibit (a) dose-limiting symptom(s) (= positive challenge) at the end of the challenge.

Table 10-9 Definition of Dose-Limiting Symptoms (per the CoFAR* grading scale, Chinthrajah et al 2022)

MILD (not typically dose limiting)	MODERATE (dose limiting)	SEVERE (dose limiting)

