The administration of study medication will precede the OFC. Investigators should apply their medical judgement when assessing if reactions occurring during the OFC or during the post-OFC observation period are symptoms caused by the food challenge or whether they are adverse events suspected to be related to the study treatment. Both adverse events suspected to be related to study treatment and allergic reactions due to the OFC should be captured on the designated CRFs, and if serious, be reported as described in Section 8.6.3 SAE Reporting. For such SAEs,

a causality assessment to either study treatment or OFC must be provided and documented together with its medical rationale.

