10.8.4 Completion of the Skin Prick Test

After measurement of skin reaction and recording them in the source document, clean the skin with alcohol to remove the ink from the marker pen on the skin.

Rarely, SPT can cause a generalized allergic reaction (e.g., hives itchy, runny nose, asthma) or even anaphylaxis. Therefore, at the completion of SPT, the participants should remain under observation at the site as per the investigator's discretion.

Adverse event reporting

If the participant experiences a systemic allergic reaction suspected to be triggered by the SPT, the event should be captured in the designated CRF. Adverse events meeting the criteria for a SAE should be reported as described in Section 8.6.3.

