2.5 Analysis supporting primary objective(s)

2.5.1 Primary safety endpoint(s)

The primary objective of the study is to assess the long-term safety and tolerability of ligelizumab in participants with food allergy for an additional three-year period after a core study.

Page 15 of 28 Study No. CQGE031G12303B

Primary endpoints are overall incidence and exposure-adjusted occurrence rates (EAOR) of treatment-emergent adverse events (TEAEs) and serious adverse events (TESAEs), however, due to early termination of the study, EAOR will not be calculated.

TEAEs are defined as events that either:

- 1) Where an AE either started after the first dose of extension study treatment and within 16 weeks after the last administered study treatment dose or
- 2) began prior to the first dose of study treatment but increased in severity (based on preferred term) within 16 weeks after the last study treatment.

All participants enrolled into the extension study, regardless of which preceding studies they came from, will be included in the safety analysis. All listings and tables will be presented by treatment dose. All data will be included in the analysis, regardless of rescue medication use.

This analysis will be based on SAF-1.

For all adverse events tables the events that the investigator classified as reactions associated to the Oral Food Challenge (OFC)or Skin Prick Test (SPT) will not be included in reporting of treatment-emergent adverse events (TEAEs).

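### SAP 2.5.1 drops all OFC and SPT reactions from TEAE reporting with no exception for serious events, so the primary TESAE count can miss SAEs that meet the protocol's definition

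*SAP*

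**What the plan says.** Protocol 9.3.1 names the overall incidence of TEAEs and treatment-emergent SAEs as primary endpoints. An event qualifies if it "started after the first dose of study treatment and within 16 weeks after the last study treatment", or if it began before the first dose and then worsened within the same limit. Cause plays no part. SAP 2.5.1 repeats this definition and then adds, for all adverse event tables, that "the events that the investigator classified as reactions associated to the Oral Food Challenge (OFC)or Skin Prick Test (SPT) will not be included" in TEAE reporting.

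The protocol's rules on challenge and skin-test reactions separate serious from non-serious events:

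- Section 10.7.5, on OFC reactions: "These events should not be reported on the Adverse Event eCRF unless they constitute an SAE".
- Section 10.7.6: "allergic reactions due to the OFC should be captured on the designated CRFs, and if serious, be reported as described" in Section 8.6.3. For these SAEs "a causality assessment to either study treatment or OFC must be provided and documented together with its medical rationale".
- Section 10.8.4, on the skin prick test: "Adverse events meeting the criteria for a SAE should be reported as described in Section 8.6.3".
- Section 8.6.3 requires reporting of "every SAE, regardless of causality, occurring after the participant has provided informed consent", and adds: "Any SAEs reported up to the last study visit will be reported in the eCRF".

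**The concern.** The SAP sentence looks like the rule in Protocol 10.7.5 without its exception for SAEs, widened to cover the skin prick test. A programmer following it would remove a serious anaphylactic reaction to a scheduled food challenge from TEAE reporting, although the event meets the timing definition stated a few lines earlier in the same section.

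TESAE incidence is a primary endpoint of a long-term safety study in which challenges and skin tests are scheduled procedures. Protocol 10.7.2 has study drug given at least 1 hour before an on-treatment challenge, so a reaction to that challenge falls inside the treatment-emergent window. The investigator must then judge whether drug or challenge caused it. Under the SAP rule that judgement decides whether the SAE enters an endpoint that the protocol defines without regard to cause. A reader of the TESAE or registry table could see a lower incidence than the protocol's definition gives and would have to find the difference in listings.

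**Working it through.** **Which outputs the rule reaches**

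| Output | Built on | Effect of the exclusion |
|---|---|---|
| TESAEs by SOC and PT (SAP 2.5.2.2) | treatment-emergent events | applies |
| AESI, including anaphylaxis (SAP 2.5.2.3) | treatment-emergent events | applies |
| Death table (SAP 2.8.2) | deaths from TEAEs | applies |
| Registry table of deaths and SAEs (SAP 2.8.1) | treatment-emergent events | applies |
| Listing of deaths (SAP 2.8.2) | all deaths in the database | does not apply |
| Listing of adjudicated anaphylaxis, cardio-cerebrovascular and neoplastic events (SAP 2.5.2.3) | adjudicated events | still listed; a summary table is optional |

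No exception for serious events appears anywhere in the visible SAP.

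**The plan's own figure.** Protocol 9.9.2 gives an exact 95% Clopper-Pearson interval of 0.12% to 3.6% for 1% of 200. The limits for x of n are the 2.5% quantile of Beta(x, n − x + 1) and the 97.5% quantile of Beta(x + 1, n − x). With x = 2 and n = 200 they are 0.12% and 3.57%, which agrees.

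**Size of the effect.** Inputs: n = 200 is the enrolment expected in SAP Section 3, not the SAF-1 size. All event counts are assumptions, because the documents give no rate of serious OFC or SPT reactions. One omitted participant with no other treatment-emergent SAE costs 1/200 = 0.5 percentage points.

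| Assumed case | Protocol definition | SAP rule |
|---|---|---|
| 1 of 4 dropped, n = 200 | 2.0% (0.55 to 5.04%) | 1.5% (0.31 to 4.32%) |
| the only one dropped, n = 200 | 0.5% (0.01 to 2.75%) | 0% (0 to 1.83%) |
| 1 of 2 dropped, dose group of 100 (equal split assumed) | 2.0% (0.24 to 7.04%) | 1.0% (0.03 to 5.45%) |

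**Exposure-adjusted incidence rate.** SAP 2.5.2.1 sets the limits at half the chi-square quantile, with 2n degrees of freedom (lower) and 2n + 2 (upper), divided by total exposure time. At an assumed 200 participant-years, 4 participants give 4/200 = 2.0 per 100 participant-years (0.54 to 5.12). Three give 3/200 = 1.5 (0.31 to 4.38). The few extra weeks at risk gained by the dropped participant are ignored.

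**Chance that any event is omitted.** For an assumed per-participant risk r of a serious OFC or SPT reaction subject to the rule, this is 1 − (1 − r)^200:

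| r | Expected omitted (200 × r) | Chance of at least one |
|---|---|---|
| 0.1% | 0.2 | 18% |
| 0.25% | 0.5 | 39% |
| 0.5% | 1 | 63% |
| 1% | 2 | 87% |

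**The case against.** The best counter-argument is that the sentence speaks of TEAEs while the SAP elsewhere names TESAEs alongside them. On that reading it only carries the protocol's data-capture rule for non-serious reactions into the tables. This does not hold: TESAEs are a subset of TEAEs, the sentence covers all adverse event tables, and no separate TESAE definition is given.

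It is also fair to say that Protocol 8.6.3, 10.7.6 and 10.8.4 govern reporting to the sponsor, not table content. The direct conflict is between SAP 2.5.1 and the timing definition in Protocol 9.3.1; the reporting sections show that the protocol treats these events as SAEs.

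Several limits stand:

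- To change overall TESAE incidence, an event must be serious, attributed to OFC or SPT, inside the window, and the participant's only treatment-emergent SAE. A Day 1 challenge before the first extension dose, a challenge more than 16 weeks after the last dose, and never-dosed SAF-2 participants are unaffected. Events attributed to study drug stay in.
- Early termination probably means few challenges. Protocol 7.5 treats participants as having discontinued treatment, and Section 7.1 then stops further challenges. SAP 2.6.1 still plans for OFC data, including early Week 156 assessments.
- Parts of the SAP are redacted, and no text is visible under Section 4, so a correcting rule cannot be excluded. The annotated CRF is not available to show how the classification is recorded.
- At the lowest assumed risk, no omission is the likeliest outcome.

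Separating challenge-provoked reactions from other TEAEs is defensible in a drug-safety summary. That supports flagging serious ones, not removing them from a primary endpoint defined by timing. For non-serious OFC reactions the exclusion follows Protocol 10.7.5.

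**Conclusion.** The concern holds on the text. SAP 2.5.1 excludes serious OFC and SPT reactions from a primary endpoint whose definition includes them, and the exclusion carries into the TESAE, AESI, TEAE-death and registry SAE tables. The loss is in summary counts; deaths and adjudicated events remain listed. The size is 0.5 percentage points per omitted participant at n = 200, or 1 point in an assumed dose group of 100. How many would be omitted is unknown and could be none. The intervals overlap widely and no hypothesis is tested, so this is a possible error in a reported safety count, not a change in a test result. It should be fixed before the tables are produced. Confidence is medium because of the redacted SAP text.

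**What to change.** Add a clause to SAP 2.5.1: OFC and SPT reactions that meet SAE criteria stay in the TESAE, AESI, death and registry tables. Either flag them by attributed trigger (OFC, SPT or study drug) or show those tables with and without them.

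A secondary documentation point: Protocol 8.3.2 and 10.8.4 send SPT reactions to a designated CRF but, unlike the OFC rule, do not keep non-serious ones off the AE eCRF. Reconcile the SAP exclusion with those sections, or record it as a change from the protocol.

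The cost is a sentence in the SAP and a flag or a few extra rows. SAEs up to the last study visit are already in the eCRF. The drawback is a slightly less favourable SAE figure, which mixes challenge-triggered with other SAEs unless the flag is used.

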2.5.2 Statistical method of analysis

Summary statistics for primary endpoints overall incidence of treatment-emergent adverse events (TEAEs) and serious adverse events (TESAEs) will be provided as follows:

The number and percentages of participants with at least one event (incidence rates)

The crude incidence rate is defined as the percentage of participants with a specific adverse event divided by the total number of participants in each study group.

Due to expected differences in exposure and follow-up due to varied duration of study participation between participants, adverse event incidence rates will be provided as "exposure adjusted AE incidence rates" in addition to the crude incidence.

2.5.2.1 Exposure-Adjusted Incidence rate and 95% confidence interval

The EAIR is defined as the number of participants with a specific event divided by the total exposure-time among the participants in the study group. That is, the EAIR is calculated as:

 $EAIR = n / \Sigma t_i$, where n is the number of participants having the i^{th} type event, and t_i is a participant's exposure time and defined as the shortest of the following:

- 1. Time to the first episode of the i^{th} type event (if the event occurs),
- 2. Time to the end of observation period, or
- 3. duration of study treatment plus the 16-week washout period (approximately corresponding to five half-lives) after last treatment dose

The total exposure time of all participants in a treatment group is Σ t_i . The EAIR is interpreted as the number of events occurring in a population per unit time. The exact Poisson 95% confidence interval for the EAIR will be provided as well, where an exact $100*(1-\alpha)\%$ confidence interval will be derived as follows (Garwood 1936, Sahai and Khurshid 1993):

- Lower confidence limit $L = \frac{0.5C_{\alpha/2,2n}}{\sum t_i}$ for n>0, 0 otherwise,
- Upper confidence limit $U = \frac{0.5C_{1-\alpha/2,2n+2}}{\sum t_i}$,

where $C_{\alpha,k}$ is the α th quantile of the Chi-square distribution with k degrees of freedom.

Whenever applicable, exposure adjusted incidence rates will be provided for the type as below:

- 1. TEAE and TESAE: Primary SOC level, PT level
- 2. Further safety analyses are defined in safety analyses (Section 2.8)

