In the CSU Phase II program, 291 participants have been exposed to ligelizumab at doses up to 72 mg, 120 mg and 240 mg SC q4w ([Investigator Brochure, 18 Ed.]). In addition, in the most recent CSU Phase III program (Studies CQGE031C2302 and CQGE031C2303), a total of 2150 patients (including 93 adolescent patients) received ligelizumab 72 mg, 120 mg, omalizumab 300 mg and placebo. Overall, no apparent dose-dependent safety signals (except for a trend in injection site reactions, which can be managed in the clinic) have been observed to date, although the number of participants studied is relatively small, in line with the development phase of the CSU program. In the asthma clinical study CQGE031B2201, there appeared to be a dose dependency of injection site reactions between ligelizumab high dose group (28.6% of 199 participants, pooled from ligelizumab 240 mg SC q2w, 240 mg SC q4w, 180 mg SC q2w, and 120 mg SC q2w treatment arms) and ligelizumab low dose group (12.5% of 40 participants, pooled from ligelizumab 36 mg SC q2w and 12 mg SC q2w treatment arms), which was comparable to omalizumab (14.5% of 131 participants). The incidence of injection site reactions was higher among all the active treatment groups compared to that of placebo (5.2% of 96 participants). Similarly, in the CSU dose-finding study (CQGE031C2201), the overall safety profile was comparable between different doses of ligelizumab (24 mg, 72 mg and 240 mg SC q4w or 120 mg single dose), omalizumab and placebo. The exceptions were adverse events (AEs) related to injection site reactions, where a possible trend of dose dependency for ligelizumab was observed. All cases of injection site reactions (except 1 case of medical significance), regardless of treatment group or doses, were non-serious, mild to moderate in severity, reversible, and did not lead to discontinuation of study treatment.

Regarding serious adverse events (SAEs), the incidence of SAEs was comparable between participants treated with ligelizumab and those receiving placebo in both asthma and CSU studies. There has been no dose dependency in SAEs observed among participants treated with different doses of ligelizumab (Study CQGE031B2201 in asthma and Study CQGE031C2201 in CSU).

Biologics can cause hypersensitivity reactions. Ligelizumab is in the same drug class as omalizumab, for which the risk and characteristics of anaphylaxis are well-characterized and are theoretically applicable to the study treatment.

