2.5.2.3 Adverse events of special interest / grouping of AEs

AEs of special interest (AESI) are defined in the latest version of the compound electronic Case Retrieval Strategy (eCRS). The classification reflects the safety topics of interest identified in the current version of the QGE031 Development Safety Profiling Plan and may be updated based on review of accumulating data. The number and percentage of participants with treatment emergent AEs of special interest will be summarized by risk category, PT and treatment. The search criteria in the latest eCRS corresponding the MedDRA version at the database lock will be used and reported in the CSR:

- Hypersensitivity reactions (including anaphylaxis)
- Cardiovascular and Cerebrovascular (CCV) events

- Neoplastic conditions
- Injection site reactions
- Serum Sickness
- Eosinophilic Conditions / Churg-Strauss Syndrome
- Parasitic (Helminthic) infections
- Thrombocytopenia

Adjudicated AEs

From the AESIs listed above, the following AEs will be adjudicated by the independent committee. The adjudicated events will be listed, and a summary table may be provided following the adjudication.

- Anaphylaxis
- Cardiovascular and Cerebrovascular (CCV) events
- Neoplastic conditions

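### Preferred-term EAIRs for injection-site reactions count injection-free time as exposure, so they are understated and depend on treatment duration; a supplementary on-treatment line would fix this

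*SAP*

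**What the plan says.** SAP 2.5.2.1 defines the EAIR as the number of participants with an event divided by total exposure time. Each participant's time is the shortest of three: "Time to the first episode of the" given event type, "Time to the end of observation period", or "duration of study treatment plus the 16-week washout period (approximately corresponding to five half-lives) after last treatment dose". The rates are planned for "TEAE and TESAE: Primary SOC level, PT level", so injection-site preferred terms are included. No exception is made for events that depend on an injection.

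The denominator window agrees with the numerator window in SAP 2.5.1, where an event is treatment-emergent if it "started after the first dose of extension study treatment and within 16 weeks after the last administered study treatment dose".

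SAP 2.4.1 defines duration of exposure differently: last dose date minus first dose date plus 28 days, expressed in weeks. It also summarises the number of doses.

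SAP 2.5.2.3 lists "Injection site reactions" among the events of special interest, but for these groups it specifies counts and percentages only: "The number and percentage of participants with treatment emergent AEs of special interest will be summarized by risk category, PT and treatment". Protocol 2.3 reports "no apparent dose-dependent safety signals (except for a trend in injection site reactions", which makes these reactions the one exception it names.

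**The concern.** SAP 2.5.2 introduces exposure adjustment because participants will differ in exposure and follow-up. A rate per unit of time serves that purpose only if the event can occur throughout the time counted. SAP 2.5.2.1 justifies its 16 weeks by about five half-lives, which is a sound reason for systemic effects. It is not a reason for a local reaction to an injection, because dosing has stopped.

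For injection-site terms the tail therefore adds time without risk. Its share is largest when treatment was short, so the same risk per dosing visit gives a lower EAIR after short treatment than after long treatment. That is the dependence the adjustment was meant to remove. The study was stopped early, and SAP 2.5.1 drops the exposure-adjusted occurrence rate, so the EAIR is the only exposure-adjusted measure left for these terms.

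**Working it through.** The SAP gives no EAIR value to reproduce, so its formula is applied to assumed exposure lengths.

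**Inputs from the documents**
- Dosing every 4 weeks, two injections per dose (protocol 6.1.3).
- SAP time limit: last dose + 16 weeks (SAP 2.5.2.1). Comparison limit: last dose + 4 weeks (SAP 2.4.1).
- Illustrative crude incidences of 12.5% and 28.6%, from the pooled low- and high-dose groups of the asthma study (protocol 2.3).

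**Assumptions**
- 100 participants per group, all with the same week of last dose (L), uninterrupted dosing and complete follow-up.
- Constant risk per dosing visit, with onset one day after a dose.

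**Step 1: quick bound.** If events are rare, almost all person-time comes from event-free participants, so the SAP rate divided by the comparison rate is about (L + 4)/(L + 16).
- L = 24: 28/40 = 0.70
- L = 52: 56/68 = 0.82
- L = 156: 160/172 = 0.93

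**Step 2: one full case** (L = 24, incidence 12.5%).
- There are 7 doses. Risk per visit is 1 − 0.875^(1/7) = 0.0189.
- The 12.5 participants with an event contribute about 148 person-weeks up to that event, under either rule.
- Event-free time, SAP rule: 87.5 × (24 + 16) = 3,500 weeks. Total 3,648 weeks = 69.9 years. EAIR = 12.5/69.9 = 17.9 per 100 participant-years.
- Event-free time to last dose + 4 weeks: 87.5 × 28 = 2,450 weeks. Total 2,598 weeks = 49.8 years. EAIR = 12.5/49.8 = 25.1.
- Shortfall: 1 − 17.9/25.1 = 29%.

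**Step 3: other durations** (EAIR per 100 participant-years, SAP rule → last dose + 28 days).

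| Week of last dose | Incidence 12.5% | Low by | Incidence 28.6% | Low by |
|---|---|---|---|---|
| 24 | 17.9 → 25.1 | 28.8% | 46.9 → 64.2 | 26.9% |
| 36 | 13.7 → 17.5 | 22.0% | 35.5 → 44.6 | 20.4% |
| 52 | 10.4 → 12.5 | 16.7% | 26.8 → 31.7 | 15.4% |
| 104 | 5.9 → 6.5 | 9.4% | 15.0 → 16.4 | 8.6% |
| 156 | 4.1 → 4.4 | 6.6% | 10.4 → 11.0 | 6.0% |

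If all reactions occur at the first dose, the shortfall is 30% (week 24), 18% (week 52) and 7% (week 156), so the timing of events matters little.

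**Step 4: dependence on duration.** With a 1% risk per dosing visit, the SAP rule gives 9.3 for a last dose at week 24 and 11.0 at week 52, a ratio of 0.85. With time ending at last dose + 28 days, both are 13.2 and the ratio is 1.00.

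**Step 5: dose contrast.** With equal exposure, the ratio of the 28.6% group to the 12.5% group is 2.62 under the SAP rule and 2.56 under the comparison rule at week 24. At week 52 it is 2.58 and 2.54.

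**Step 6: gaps.** Under protocol 4.1.2.1, a participant treated to week 52 may stop as a maximum responder and restart after a failed challenge at week 68 or week 104. Beyond the 28 days credited to the week 52 dose, that adds about 68 − 52 − 4 = 12 or 104 − 52 − 4 = 48 injection-free weeks. They lie between first and last dose, and the 2.4.1 formula does not subtract them. The table omits this.

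**The case against.** The rule is a usual one for adverse events, and numerator and denominator share the same window, so the EAIR correctly estimates the quantity it defines. It is low only against a measure of risk while being injected. The output affected is also narrow. Injection-site reactions as a group are summarised by count and percentage, which the denominator cannot touch. The protocol's 28.6% and 12.5% are crude figures whose like-for-like counterpart here is intact. The analysis is descriptive, with no hypothesis test, and SAP 2.5.2.2 already presents events by dose and cumulative duration of exposure.

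All of this stands and limits the point. It does not remove it: preferred-term EAIRs for these reactions will still be produced, and the half-life rationale does not fit them.

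Three stronger readings are tempting and not supported:
- A reader might infer that the rule hides a dose effect. Step 5 shows the dose ratio hardly moves under balanced exposure, and nothing in the documents shows imbalance between doses. Protocol 2.3 speaks of a trend or possible trend, not an established effect.
- A reader might count all 16 weeks as excess. The first 4 lie within the SAP's own exposure duration. Participants with a reaction stop at that event, and incomplete follow-up shortens the tail, so 12 weeks is a maximum for the tail.
- A reader might infer a loss of about 40%. That needs a last dose at week 12, which no passage supports.

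**Conclusion.** The point holds as a limited one. For injection-site preferred terms, the single time rule understates the EAIR relative to on-treatment time and makes it depend on treatment duration. The shortfall is about 27-29% for a last dose at week 24, 15-17% at week 52 and 6-7% at week 156.

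These figures assume complete follow-up and no interruptions. Shorter follow-up would reduce them. Maximum-responder gaps would add further dilution. The durations are assumptions. The only hint in the SAP is the 380-day rule in 2.6.1, which suggests that some participants ended within about a year. The benchmark is also a choice: reactions placed one day after a dose leave event-free time even within 28 days, and against time to the last dose alone the week 52 shortfall would be 20-22%.

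The absolute rates, and any comparison across groups with unequal treatment duration, need care. Crude incidence and a balanced comparison of doses do not.

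**What to change.** Keep the standard EAIR for all terms. In SAP 2.5.2.1 add a supplementary line for injection-site reaction preferred terms, by dose, that counts only on-treatment time: from each dose to 28 days after it, with protocol-mandated interruptions removed. Apply the same limit to onset in the numerator, so that no event is counted outside the time at risk.

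Alternatively or in addition, report the number of dosing visits with an injection-site reaction per 100 dosing visits, by dose, using the dose counts already planned in SAP 2.4.1. Define one visit as two injections, since one of the two is placebo in the 120 mg arm, and count a visit once however many reactions follow it. This measure is unaffected by washout and gaps.

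The SAP should also say whether the treatment duration in 2.5.2.1 already includes the 28 days of 2.4.1. If it does, the tail is 20 weeks after the last dose, not 16.

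The cost is one extra table line from data already collected, and a footnote explaining that the time base differs from other terms. The supplementary rate will look less favourable than the standard EAIR.
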